9.7.1.5.1. Primary Efficacy Analysis

The key efficacy measure is best-corrected visual acuity score of the study eye using the ETDRS as assessed by certified Investigator or designee. The endpoint is the change from baseline in ETDRS letters at Week 4, so scores from Day 1 and Week 4 will be analyzed. Final scores will be calculated as Week 4 minus Day 1 BCVA letter counts. A positive result will indicate more letters gained following AG-73305 injection, while a negative score indicates worsening of vision. Observed and change from baseline in BCVA letter count at other visits will be summarized in a similar fashion to the key efficacy measure.

In addition, change from baseline in BCVA letter count as measured by ETDRS at each visit and the proportion of study eyes with ≥ 5 , ≥ 10 , and ≥ 15 BCVA letter increase from baseline will be analyzed.

9.7.1.5.2. Secondary Efficacy Analyses

Observed and change from baseline in CST as measured by SD-OCT at Week 1, 4, 8, 12, 16, 20 and 24 will be presented. A change from baseline in CST will indicate a positive response if the treatment difference is < 0 . Observed and change in intraretinal and subretinal fluid volumes, ELM and EZ by SD-OCT at each visit will also be presented. The presence of posterior vitreous detachment will be summarized by frequency and percentage.

Observed and change from baseline in FAZ and CD of the superficial and the deep capillary plexuses will be presented, as measured by OCT-A at the Baseline Visit, Week 4, and Week 24.

Observed and change from baseline in DRSS will be presented, assessed via color fundus photography at the Baseline Visit, Week 4, and Week 24.

Time from Day 1/Baseline to receipt of rescue medication in the study eye will be analyzed using Kaplan-Meier time-to-event analyses. Follow-up is measured to the earliest instance of receipt of rescue therapy in the study eye for patients receiving rescue therapy. Otherwise, patients are censored at the date they complete or discontinue the study. In addition, reasons for rescue and use of rescue medication by visit will be summarized by frequency and percentage. Rescue will be included at Visit X if the date rescue is provided is on or after Visit X and before Visit X + 1.

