- h. IOP measurement will be performed prior to and after AG-73305 injection at Baseline/Day1. After injection, IOP will be measured within 15 minutes using a tono-pen or tono-pen like device. If IOP >30mmHg, repeat IOP measurement at 15±5 minutes post injection until pressure is reduced
- i. Color fundus photos, OCT-A and SD-OCT images will be submitted to a reading center for grading; not required for eligibility
- j. OCT-A is to be performed at baseline and at the visit (OU) when **Rescue** treatment is given. OCT-A is to be performed prior to the rescue treatment
- k. Dilated fundus exam
- l. Prednisolone acetate 1% ophthalmic suspension will be provided to patients, who will be instructed to prophylactically treat the study eye QID 2 days prior to the Baseline visit. Patients will be instructed to taper based on the Day 2 follow-up visit
- m. Within 15 minutes following intravitreal injection, a post-injection assessment will be done, including checking for count fingers or hand motion vision
- n. At selected sites, blood (~10 mL) will be collected for plasma drug monitoring on Day 1 pre-dose (all Cohorts), 1 hour (Cohort 1 and 2 only), 3 hours (all Cohorts), 8 hours (all Cohorts) and 24 hours post dose (Cohort 3 and 4 only), Week 1 (all Cohorts), and Week 4 (all Cohorts) in approximately 2-4 patients.
- o. ~20 mL of blood will be collected on Day 1 pre-dose and Weeks 1, 4, 8 and 24 from all patients for anti-drug antibody assessments.

Additional examinations and unscheduled visits can be included as safety concerns arise.

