9.5.1.3.2. Secondary Efficacy Assessments

Dilated color fundus photography will be performed OU at the Baseline Visit, in the SE at Week 4, and OU at Week 24 to assess diabetic retinopathy severity score (DRSS).

Spectral Domain Optical Coherence Tomography (SD-OCT) will be performed OU at each in-clinic visit (Heidelberg Spectralis, dense scan). SD-OCT will assess central subfield thickness (CST), ellipsoid zone (EZ), external limiting membrane (ELM), intraretinal and subretinal fluid volume, and posterior vitreous detachment.

OCT Angiography (OCT-A) will be performed OU at the Baseline Visit, in the SE at Weeks 4 and 24, and OU at the visit when Rescue treatment is given. OCT-A will assess foveal avascular zone (FAZ) and foveal capillary density (CD) (superficial and deep capillary plexuses).

Color fundus photos and SD-OCT and OCT-A images will be submitted to a central reading center for grading.

Time to rescue medication will be assessed. Rescue medication will be standard-of-care anti-vascular endothelial growth factor (VEGF) administered by intravitreal injection (IVT) in the

study eye. Rescue medication is allowed at the Week 4 visit or later in patients meeting any of the criteria outlined in the protocol Section 6.5.3.

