The nominal visits listed in the eCRF will be used in the summaries. In general, unscheduled visits will not be summarized in tables unless otherwise noted.

Missing Dates

Missing dates that occur for prior or concomitant medications or adverse events will be queried for a date. If no date is obtained, the following imputation rules will apply:

- For start dates, if the given year (or year-month) is the same as study drug administration, the start date will be imputed as study drug administration date; otherwise, missing month-day (or day) will be imputed as '01-01' (or '01').
- For stop dates, missing months will be imputed as '12' and missing days will be imputed as the last day of the month. If this creates a date after discontinuation/completion, the date of discontinuation/completion will be used.

Imputed dates will only be used to classify events or medications, such as occurring before or after the start of treatment. Imputed dates will only be used in tables. Listings will display the available date data.

Interim Analysis

No formal interim analysis is planned. However, as the study is open-label, safety and efficacy data will be periodically reviewed and summarized for assisting the Safety Review Committee with their assessments.

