9.7.1.5. Analysis of Efficacy

Summary descriptive statistics will be presented for all study visits at which efficacy data are collected. Efficacy analyses will be presented by cohort for the study eye using the FAS population. Data for efficacy assessments for the non-study eye will be provided in listings.

All efficacy data will be censored (set to missing) on or after the earliest instance of rescue therapy when summarized in tables. All data will be presented in listings.

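### The OCT-A scan required before rescue has no planned summary, so the Week 24 OCT-A table describes only never-rescued eyes

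*SAP*

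**What the plan says.** **Collection.** SAP 9.5.1.3.2 schedules OCT-A in both eyes at Baseline, then "in the SE at Weeks 4 and 24, and OU at the visit when Rescue treatment is given". Footnote j of the Protocol's Schedule of Activities (1.3) fixes the order on the rescue day: "OCT-A is to be performed prior to the rescue treatment". Footnote j of SAP Table 3 repeats this. The images go to the central reading center. Rescue is possible from the Week 4 visit onward (Synopsis, both documents).

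**Analysis.** SAP 9.7.1.5.2 presents the OCT-A measures, observed and as change from baseline, "as measured by OCT-A at the Baseline Visit, Week 4, and Week 24". It does not mention the rescue-visit scan.

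**Rules that decide what reaches a table.**
- SAP 9.7.1.5 opens by promising descriptive statistics at every study visit where efficacy data are gathered.
- The same section then states: "All efficacy data will be censored (set to missing) on or after the earliest instance of rescue therapy when summarized in tables". It adds: "All data will be presented in listings".
- SAP 9.7.1, Visit Windows, says that in general "unscheduled visits will not be summarized in tables unless otherwise noted".
- SAP 9.7.1, Missing Data and Outliers, restricts analyses to observed values, so nothing is carried forward.

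**The concern.** OCT-A is one of three measures named in the efficacy hypothesis (Protocol Synopsis), and duration of effect is a stated objective. After Week 4 the OCT-A analysis has one remaining time point, Week 24. An eye rescued in between contributes nothing there, because its later data are set to missing. The Week 24 scan may not even be taken: the Synopsis requires follow-up of a rescued patient only to Week 12 or to 4 weeks after rescue, whichever is later.

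Rescue is triggered by letter loss, CST increase or worsening proliferative retinopathy, so eyes leave the table because of how they fared. BCVA and CST are summarized at every visit, so rescued eyes still appear in the rows before rescue. OCT-A has no intermediate rows. The one scan that would describe a rescued eye late in its drug-only period is mandated and graded, yet has no defined place in a table.

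**Working it through.** No figure in the plan bears on this point, so the check sets the rules side by side and then illustrates the size.

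**Step 1: the gap.** Scheduled post-baseline OCT-A falls on Day 28 and Day 168, which are 168 − 28 = 140 days apart. Four visits lie between (Weeks 8, 12, 16, 20). The only OCT-A required there is the pre-rescue scan.

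**Step 2: what reaches the tables.** The censoring rule does not say whether it works by date or by clock time. The neighboring rules in 9.7.1.5.2, on time to rescue and on rescue by visit, work by date. Both readings are shown.

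| First rescue at | Compared by date | If same-day pre-injection data are kept |
|---|---|---|
| Week 4 visit | Week 4 and Week 24 both blank | Week 4 kept, Week 24 blank |
| Week 8, 12, 16 or 20 visit | Week 4 kept, rescue scan and Week 24 blank | Week 4 kept; rescue scan tabulated only if the opening sentence of 9.7.1.5 overrides the list in 9.7.1.5.2; Week 24 blank |
| Unscheduled visit after Week 4 | Week 4 kept, rescue scan untabulated, Week 24 blank | The same, because of the unscheduled-visit rule |
| Week 24 visit | Week 4 kept, Week 24 blank | Both kept |
| Never | Both kept | Both kept |

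Two results follow. Adding the rescue visit to the list in 9.7.1.5.2 would not be enough, since the censoring rule could still blank the scan. And by date, an eye rescued at Week 4 has no post-baseline OCT-A in any table.

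**Step 3: size.** Inputs: about 25 patients (Synopsis) and 3–8 per cohort (SAP 9.7.2). The rescue proportion r, after the Week 4 visit and up to Week 24, is **assumed**. The figures take no rescue at Week 4, no dropout and every scan gradable.

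- Eyes left at Week 24 = 25 × (1 − r)
- Eyes regained by a pre-rescue row = 25 × r
- Eyes left in a cohort of 6 = 6 × (1 − r)
- Chance that a cohort of n has no eye left = r^n, if rescues are independent

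| Assumed r | Left of 25 | Regained | Left of 6 | No eye left, n = 3 | n = 6 | n = 8 |
|---|---|---|---|---|---|---|
| 0.30 | 17.5 | 7.5 | 4.2 | 0.027 | 0.001 | <0.001 |
| 0.50 | 12.5 | 12.5 | 3.0 | 0.125 | 0.016 | 0.004 |
| 0.70 | 7.5 | 17.5 | 1.8 | 0.343 | 0.118 | 0.058 |

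**The case against.** The best defense has four parts.

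1. **The general sentence may already cover the scan.** The opening of 9.7.1.5 reaches every visit with efficacy data, which could include a rescue scan at Week 8, 12, 16 or 20. This stands in part. A reader might infer that the scan has no row however the post-rescue rule is applied; for scheduled visits the documents do not establish that. They do show a general sentence and a narrower list that conflict, and a censoring rule with no stated exception for assessments made before the injection.

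2. **Nothing is hidden.** The scan is listed, the Week 4 value remains for eyes rescued later, N accompanies each continuous summary, and time to rescue, reasons and rescue by visit are tabulated. All true. So it would be wrong to say that eyes rescued after Week 4 yield no later capillary data; the loss is from the tables. A listing still gives no cohort summary.

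3. **The selection comes from the general censoring rule.** It affects BCVA, CST and DRSS at Week 24 as well. This stands. What is particular to OCT-A is that there are no intermediate rows while an extra scan is required at rescue.

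4. **A pooled row is not like for like.** Rescued eyes would be scanned when they meet a worsening criterion and the others at about Day 168. This stands, and is why the row should be supplementary.

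The study is also small and descriptive, with OCT-A a secondary measure, which limits the consequence.

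**Conclusion.** The point holds as a gap in the planned summaries and is worth correcting. Under the date reading, the Week 24 OCT-A table describes only never-rescued eyes, and the pre-rescue scan is confined to listings. The size depends entirely on the rescue proportion, which the documents do not give; over the assumed 30–70% range, 17.5 down to 7.5 of 25 eyes remain.

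Three stronger readings are not supported:
- **That the Week 24 table favors the drug.** The subset is outcome-dependent, but there is no comparator, and nothing in the documents gives the direction or size of any bias in foveal avascular zone or capillary density.
- **That the scan's purpose is a drug-only reading.** Its timing is consistent with that, but neither document states a purpose, and it covers both eyes although efficacy is analyzed in the study eye.
- **That a new row brings back all 25 eyes.** The regained counts are ceilings, before dropouts and ungradable scans, and they assume no rescue at Week 4.

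**What to change.** 1. **SAP 9.7.1.5:** state that assessments made before the rescue injection on the date of first rescue count as pre-rescue and are not set to missing. This also keeps the Week 4 scan of an eye rescued at Week 4. Reconcile the section's opening sentence with the visit list in 9.7.1.5.2.
2. **SAP 9.7.1.5.2:** keep the Week 4 and Week 24 rows. Add a supplementary row by cohort: change from baseline at the last OCT-A before rescue. Define it as the pre-injection scan at the first rescue visit (scheduled, including Week 4, or unscheduled) or, for an eye never rescued, the Week 24 scan. Report the study day of the scan and the numbers of rescued and never-rescued eyes.
3. **SAP 9.7.1, Visit Windows:** exempt this scan from the unscheduled-visit rule.

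**Cost.** SAP wording and one table row; the scans are already required and centrally graded. Scan times vary and depend on outcome, so the row is descriptive and must be read beside its study day. Item 1 is general, so same-day pre-injection BCVA and CST values would also stay in the efficacy tables. The parallel censoring rule in SAP 9.7.1.6 should be checked so that BCVA is handled consistently in the efficacy and safety tables.

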#### **Response Measures:**

##### *Safety assessments:*

- Adverse Events (AEs)
- ETDRS BCVA
- Intraocular pressure (IOP)
- Slit lamp biomicroscopy
- Dilated fundus exam (DFE)
- Crystalline lens assessment using AREDS scale
- Post-injection assessment
- Laboratory evaluation (hematology, serum chemistry and urinalysis)
- Electrocardiogram (ECG)
- Vital signs
- Physical examination
- Pregnancy test

*Efficacy assessments:*

- Improvements in ETDRS BCVA
- SD-OCT (Heidelberg Spectralis, dense scan) as measured by Central Reading Center (CRC)
  - Central subfield thickness (CST)
  - Ellipsoid zone (EZ)
  - External limiting membrane (ELM)
  - Intraretinal and subretinal fluid
  - Posterior vitreous detachment
- OCT-A as measured by CRC
  - Foveal avascular zone (FAZ)
  - Foveal capillary density (CD) (superficial and deep capillary plexuses)
- Diabetic retinopathy severity score (DRSS) assessed via color fundus photography
- Time to rescue medication

*Pharmacokinetics:* Plasma concentrations of AG-73305.

*Immunogenicity:* Serum levels of anti-AG-73305 antibodies (using binding and neutralizing antibody assays, if available).

**Study Population:** Approximately 25, adult male or female patients with center involving DME in the study eye will participate in the study, including a sentinel patient in each of 4 dose cohorts (see [Figure 1](#)).

**Phase:** 2a

**Description of Sites:** Approximately 8 sites in the United States will enroll patients.

**Description of Study Treatment:** AG-73305 is a humanized IgG1 Fc-fusion protein that targets vascular endothelial growth factors, placental growth factors and integrins. AG-73305 is a clear solution formulated in a 40 mg/mL concentration for intravitreal injection. Ascending doses of a single injection of AG-73305 will be assigned by cohort to 0.5, 1, 2, and 4 mg or until the maximally tolerated (or maximum administered) dose has been reached (see [Table 1](#)).

**Rescue Medication** will be standard-of-care anti-vascular endothelial growth factor (VEGF) administered by IVT in the study eye. Rescue medication is allowed at the Week 4 visit or later in patients meeting any of the following criteria:

- Loss of > 10 ETDRS letters from a previous best study visit with worsening of intraretinal or subretinal fluid observed by SD-OCT and judged by the Investigator to be the cause of the BCVA loss.

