- Loss of > 5 ETDRS letters at 2 consecutive visits (one can be unscheduled) from a previous best study visit due to worsening of DME.

- An increase in CST  $> 75 \mu\text{m}$  from a previous best study visit which remains consistently  $> 75 \mu\text{m}$  from the previous best study in two consecutive visits, as assessed by SD-OCT. The later visit can be an unscheduled visit if determined to be necessary by the Investigator.
- An increase in CST  $> 50 \mu\text{m}$  from a previous best study visit, as assessed by SD-OCT and a loss of  $> 5$  ETDRS letters, which remains consistently  $> 50 \mu\text{m}$  and loss  $> 5$  ETDRS letters from the previous best study in two consecutive visits. The later visit can be an unscheduled visit if determined to be necessary by the Investigator.
- Progression of or worsening of proliferative diabetic retinopathy.

Patients will be followed for at least 4 weeks after Rescue medication administration or through Week 12, whichever is greater.

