9.7.1. Statistical and Analytical Plans

General Conventions

Summary statistics for the data collected during this study will be presented to give a general description of the patients studied. Data from all sites will be combined in the computation of these descriptive summaries. Categorical variables will be summarized by the frequency and percentage of patients in each category. Continuous variables will be summarized using N, mean, standard deviation (SD), median, minimum, and maximum values.

Number of patients, minimums, and maximums will be calculated to the same number of decimal places as the source data. Means, medians, standard deviations, and quartiles will be calculated to one more decimal place than the source data. Percentages will be calculated to the nearest one decimal place. Zero count cells will be displayed as “0” with percentage of (0%). Unless otherwise noted, summaries will be performed by the treatment group and presented in the order of: AG-73305, 0.5 mg; AG-73305, 1 mg; AG-73305, 2 mg; AG-73305, 4 mg.

Baseline values will be defined as the last measurement prior to dosing of study medication. Ocular measurements will use the most recent measurement for each eye.

Numeric laboratory, pharmacokinetic, and immunogenicity data may be recorded at limits of detection (with a ‘<’ or ‘>’ sign, e.g., < 0.1 or > 0.1). To summarize laboratory data, the original value will be converted to one unit less or more at the level of measured precision (e.g. 0.4 in the case of < 0.5 and to 0.6 in the case of > 0.5). For pharmacokinetic data, for Time = 0 (predose), any result that is below the level of quantitation (BLQ) is set to zero; all other timepoints are set to missing for any computations. For immunogenicity, any titer < Value (a negative result) is set to zero. Summary tables for immunogenicity titer will not include these negative results.

The actual values will be presented in the data listings.

All data collected in this study will be presented in individual patient data listings for all patients.

Computations for all results will be performed using SAS (Version 9.4, SAS/STAT 15.2) computer software package (SAS Institute, Inc, 2013, 2020), unless otherwise specified.

Strata and Covariates

Not applicable.

Subgroups

Not applicable.

Multiplicity

Not applicable.

Missing Data and Outliers

Every attempt will be made to capture all study data. All analyses will utilize observed data only.

Visit Windows

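### The Week 24 DRSS table drops eyes because of the outcome it measures: worsening proliferative retinopathy triggers rescue, and rescue sets DRSS to missing

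*SAP*

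**What the plan says.** Rescue is opened by the Protocol synopsis (Section 1.1, Rescue Medication): "Rescue medication is allowed at the Week 4 visit or later in patients meeting any of the following criteria". Five criteria follow. Four concern visual acuity, edema or central subfield thickness. The fifth is "Progression of or worsening of proliferative diabetic retinopathy". The SAP synopsis repeats the list.

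DRSS is a secondary efficacy measure graded from fundus photographs. SAP Section 9.5.1.3.2 fixes the times: "Dilated color fundus photography will be performed OU at the Baseline Visit, in the SE at Week 4, and OU at Week 24". The protocol's schedule of activities agrees, and its last column also covers early termination. OCT-A is treated differently. It is additionally required "OU at the visit when Rescue treatment is given", and footnote j of the schedule adds "OCT-A is to be performed prior to the rescue treatment". Neither place asks for a fundus photograph at rescue.

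Two analysis rules then apply. SAP Section 9.7.1.5 says "All efficacy data will be censored (set to missing) on or after the earliest instance of rescue therapy when summarized in tables", and the general conventions in Section 9.7.1 say "All analyses will utilize observed data only". The DRSS analysis itself is the single sentence "Observed and change from baseline in DRSS will be presented, assessed via color fundus photography at the Baseline Visit, Week 4, and Week 24". Section 9.7.1.5.2 also plans a tabulation of reasons for rescue, and Section 9.7.1.5 keeps all data in listings.

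**The concern.** Censoring at rescue usually removes eyes for reasons that are at most related to the measure being summarized. Here one trigger is a form of the very worsening that DRSS is meant to record. An eye that progresses can be rescued because it progressed and then leave the DRSS table for that reason.

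The planned Week 24 table could show a cohort as stable although some eyes progressed, with nothing in the table to tell the reader so. Cohorts have 3 to 8 patients (SAP Section 9.7.2), so a single removed eye can change a cohort's summary. Nothing is tested, so what is at stake is how the drug's effect on retinopathy is read, not an error rate.

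**Working it through.** **The plan's own figure.** The documents give no number for DRSS or for rescue. The only computed figure is SAP Table 2, the chance of at least one event in n patients, 1 − (1 − p)^n. At p = 0.10 and n = 8 this is 1 − 0.9^8 = 0.570, as printed, and all 24 cells reproduce. The same formula gives the chance that a cohort has at least one patient rescued for worsening PDR. The per-patient risk is an assumption.

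| Assumed risk | n = 3 | n = 6 | n = 8 | n = 25 (whole study) |
|---|---|---|---|---|
| 5% | 0.143 | 0.265 | 0.337 | 0.723 |
| 10% | 0.271 | 0.469 | 0.570 | 0.928 |

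**What happens to an eye rescued for worsening PDR.**

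| Day of rescue | Scheduled photographs | DRSS values left in tables |
|---|---|---|
| Week 4 visit | Baseline, Week 4 (same day), Week 24 or exit | Baseline |
| Between Week 4 and Week 24 | Baseline, Week 4, Week 24 or exit | Baseline, Week 4 |
| Week 24 visit | Baseline, Week 4, Week 24 (same day) | Baseline, Week 4 |

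No row keeps a DRSS value from the rescue day or later, because the rule covers the day of rescue as well as the time after it. Follow-up after rescue may also end before Week 24: the synopsis requires at least 4 weeks after rescue or through Week 12, whichever is greater.

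**Effect on the Week 24 table.** Three assumed quantities are needed:
- w: the true share of eyes with worse DRSS at Week 24;
- s: the share of those eyes removed by rescue for any reason;
- r: the share of all other eyes removed by rescue.

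Share shown as worsened = w(1 − s) / [w(1 − s) + (1 − w)(1 − r)].

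This equals w when s = r, falls below w when s > r and rises above it when s < r. The PDR trigger adds to s. The edema triggers can add to either. For example, w = 0.10, s = 0.50, r = 0 gives 0.05 / (0.05 + 0.90) = 5.3%.

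| True w | s = 0.25, r = 0 | s = 0.50, r = 0 | s = 0.75, r = 0 | s = 1, r = 0 | s = 0.50, r = 0.20 | s = 0.25, r = 0.50 |
|---|---|---|---|---|---|---|
| 5% | 3.8% | 2.6% | 1.3% | 0% | 3.2% | 7.3% |
| 10% | 7.7% | 5.3% | 2.7% | 0% | 6.5% | 14.3% |
| 20% | 15.8% | 11.1% | 5.9% | 0% | 13.5% | 27.3% |

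The last column shows the reverse case: if edema-driven rescue falls mostly on eyes without DRSS worsening, the table overstates worsening.

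**Two illustrative cohorts of 6.**
- Two eyes rescued for PDR, one unrescued eye improved, three unchanged. The planned table shows 0/4 worse and 1/4 (25%) improved. Over all treated it is 2/6 (33%) worse and 1/6 (17%) improved.
- One eye rescued for PDR, two eyes with improved DRSS rescued for retinal thickness, three unchanged. The planned table shows 0/3 worse and 0/3 improved. Over all treated it is 1/6 worse and 2/6 improved.

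In both cohorts the planned table shows no worsening although it occurred. In the second it hides more improvement than worsening.

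**The case against.** The strongest case for the plan has four parts.

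- Censoring has a proper purpose: it stops the effect of rescue anti-VEGF treatment from being credited to AG-73305 in the Week 24 DRSS. This stands, and it is why the censored table should be kept.
- The events are not lost. Reasons for rescue are tabulated, time to rescue is analyzed, and all data are listed; with about 25 patients, each such eye can be found. This also stands, but none of it enters the DRSS summary. Safety tables are censored at rescue in the same way (SAP Section 9.7.1.6), so a fundus examination on the rescue day leaves those tables too.
- DRSS is one of many descriptive secondary measures; the key endpoint is BCVA at Week 4. This limits the weight of the point but does not answer it.
- The protocol's full rescue section (6.5.3, cited by the SAP) is not in the text reviewed, so a rescue-visit photograph required only there cannot be excluded. The censoring rule would still keep it out of the tables.

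A reader might infer more than the documents support:

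- That the bias always favors the drug. It need not, because four of the five triggers can also remove eyes whose DRSS improved or did not change.
- That every worsened eye is removed. Rescue is allowed, not required; DRSS worsening that is not PDR worsening is no trigger; and Week 4 values are lost only if rescue is given that day.
- That rescued patients are never photographed again. The schedule includes an early-termination photograph, although the tables exclude it.
- That DRSS will be averaged as if its steps were equal. Section 9.7.1.5.2 does not say so.

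**Conclusion.** The point holds in a limited form. Missingness in the Week 24 DRSS summary depends on the outcome, because a rescue trigger is itself a form of that outcome and the plan has no rule that brings the event back into the table. The summary will tend to understate worsening. The net direction rests on whether worsened eyes are removed more often than other eyes (s above r), and the documents do not settle this.

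The size is unknown. With no other rescue, a true 10% would appear as anything from 7.7% down to 0% as s runs from 0.25 to 1; all of these rates are assumed, and the cohorts of 6 are illustrations only. The loss falls mainly at Week 24 and affects description only. This is a worthwhile, inexpensive improvement to a supportive measure; it does not bear on the key endpoint.

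**What to change.** In SAP Section 9.7.1.5.2, add a Week 24 DRSS table by cohort, with all Full Analysis Set patients in the cohort as denominator and one line per patient:

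- improved, unchanged or worsened, in graded scale steps from baseline, before any rescue;
- rescued for progression or worsening of PDR;
- rescued for another reason;
- not assessed.

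Below these lines, give a combined total of graded worsening plus PDR rescue. State that a patient rescued on or before the Week 24 visit goes to a rescue line, and that a patient with several recorded reasons goes to the PDR line if PDR is among them. Keep the observed-only censored table as supportive.

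The cost is SAP wording and one table. Reasons for rescue are already planned for summary, so no new data are needed and no visit or rescue criterion changes. The downside is that the combined total mixes centrally graded worsening with the investigator's judgment; the separate lines show how much of each it contains.
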